1.1 SYNOPSIS

Title:	Feasibility of Measuring Volume of Inspiration Via Non-Invasive Motion Sensors
Study Description:	This protocol is a basic physiologic proof-of-concept study enrolling normal volunteers to determine the feasibility of measuring volume of inspiration from chest wall motion measured via non-invasive thoracic motion sensors. The motion sensors are not medical devices because they are not intended to diagnose a disease or condition or to cure, mitigate, treat or prevent disease. Since motion sensors are not being evaluated for diagnostic purposes or being studied themselves within the context of this protocol and are only intended to collect physiological data, they are not to be considered investigational. The data collected in this feasibility study will not contain any personally identifiable information (PII). In this study, healthy participants will complete a total of approximately 18 measured breaths through a traditional incentive spirometer while wearing small, non-invasive motion sensors on their thorax at approximately the level of the 9 th and 10 th ribs unilaterally or bilaterally. The incentive spirometer is an FDA approved medical device. This study does not aim to study the safety or effectiveness of this device but rather utilize the device as a tool to measure volume of inspiration. The waveform data collected from the devices with each breath will then be analyzed with the intention to develop an algorithm that could convert chest wall motion to a discrete volume of inspiration in real time. Total enrollment time will be about 10-30 minutes per participant.
Objectives:	
Primary:
 
To collect chest wall motion data corresponding to various volumes of inspiration from a non-invasive wearable device.
 
Secondary:
 
To develop an algorithm which can convert chest wall motion to volume of inspiration and assess the algorithm using cross-validation strategy.

Endpoints:	
Primary:
 
A database of motion waveforms corresponding to each measured volume of inspiration via traditional incentive spirometer.
 
Secondary:
 
A cross-validated algorithm that converts chest wall motion to volume of inspiration.

Study Population:	Healthy volunteers of both sex and demographic groups who are ages 18 and older.

Abbreviated Title: Wearable Incentive Spirometry

Version Date: 09/08/2025

[figure not shown]

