1.2 SCHEMA

Participation Flow Diagram

Flow diagram alt text:

- Participants will be consented at the start of the meeting and provided a study ID to ensure patient confidentiality.
- Each participant will then fill out a form with their study ID, age, sex, height, weight.
- The small motion sensor will then be placed unilaterally or bilaterally on the patient's thorax at approximately the level of the 9th and 10th ribs at the mid-axillary line using hypoallergenic double-sided adhesive tape.
- With the motion sensor in place, the participant will then take breaths through a traditional FDA approved incentive spirometer. They will ideally complete three breaths at each of the following volumes: 250mL, 500mL, 1000mL, 1500mL, 2000mL, and 2500mL.
- Upon completion, the motion sensor will be removed, and the participant will be free to go with no future scheduled appointments or follow-up.

INTRODUCTION

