The continual advancements of digital health technologies and artificial intelligence present a compelling opportunity to address these gaps. Some efforts have been made by other groups to correlate chest wall motion with lung function, particularly in the asthma and apnea monitoring spaces. One group was successful in measuring respiration rate and lung volume using wearable strain sensors on a small cohort of volunteers. Others have detected respiratory rate via acoustic adhesive sensors on the neck [14] or detected changes in respiratory effort during sleep via an elastic band around the thorax and corresponding sensor measuring stretch patterns [15]. It is possible that we might identify unique patterns in chest wall motion via motion sensors adhered to the patient's thorax to easily measure and track volume of inspiration and respiratory effort post-operatively. This technology could open a door to improved IS compliance and may result in decreased nursing burden and improved post-operative management. If successful, it is possible that a wearable motion sensor could serve as a substitute for incentive spirometry with features to improve patient compliance, facilitate longitudinal IS data collection, and reduce burden on nursing staff who continuously have to provide incentive spirometers and remind patients to use them.

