1.17 STUDY INTERVENTIONS(S) OR EXPERIMENTAL MANIPULATIONS(S) ADMINISTRATION

1.17.1 Study Intervention or Experimental Manipulation Description

All participants will be included in the interventional or experimental group for this study. There is no control group. The intervention includes the application of a small motion sensor placed on the patient's chest at approximately the level of the 9th and 10th ribs at approximately the mid-axillary line using hypoallergenic double-sided adhesive tape. With the motion sensor in place, the participant will then take breaths through a traditional FDA approved incentive spirometer. They will ideally complete three breaths at each of the following volumes: 250mL, 500mL, 750mL, 1000mL, 1500mL, 2000mL, and 2500mL. Upon completion, the motion sensor will be removed, and the participant will be free to go with no future scheduled appointments or follow-up.

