1.26 STUDY EVALUATIONS & PROCEDURES

All patients consented for participation will undergo the following procedures:

1. Recording self-reported age, sex, height, and weight.
2. Application of the motion sensor using a medical grade double sided adhesive.
3. While seated, each participant will ideally take three breaths at each of the following volumes through a traditional FDA approved incentive spirometer: 250mL, 500mL, 1000mL, 1500mL, 2000mL, and 2500mL. The participants will hold each breath for approximately 5 seconds before exhaling.
4. Data collection will include motion data transmitted from the motion sensor to a secure NIH server.

Abbreviated Title: Wearable Incentive Spirometry

Version Date: 09/08/2025

None of this data will be transmitted back to the participants themselves. All findings associated with this study will, however, be made publicly available upon the completion of this study.

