1.33.3 Analysis of the Secondary Endpoint(s)

Secondary Endpoint: A cross-validated algorithm that converts chest wall motion to volume of inspiration.

Motion waveforms will be annotated by volume of inspiration. A model will be fine-tuned on these sequences, learning to recognize subtle deteriorations in the waveform that correspond with varying volumes of inspiration. The pre-trained AI models will be validated for each task (e.g., each measured volume of inspiration). This will be done using a validation set and then test using a held-out test set wherein no parameter optimization is performed. Different validation and test sets will be generated using a cross-validation strategy such as stratified K-fold.

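### The accuracy figure planned in 1.33.3 cannot separate stable person-to-person differences in chest motion per litre from breath-to-breath error, because the split unit is unstated and no calibration or repeatability analysis is planned

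*Combined protocol and SAP*

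**What the plan says.** Section 1.26 plans that "each participant will ideally take three breaths at each of the following volumes", and the synopsis expects that "healthy participants will complete a total of approximately 18 measured breaths through a traditional incentive spirometer". Section 1.7 accepts one attempt per volume as the minimum, so repeats are intended but not guaranteed.

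The synopsis states the aim as to "develop an algorithm that could convert chest wall motion to a discrete volume of inspiration in real time". For the assessment, 1.33.3 says: "This will be done using a validation set and then test using a held-out test set wherein no parameter optimization is performed". It adds that validation and test sets will come from a cross-validation scheme, with stratified K-fold as an example. It does not give the unit that is split (person or breath), the number of folds or the stratifying variable. Section 1.33.1 says only that the model is fine-tuned and validated on the subjects in the dataset.

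Validation is described for each measured volume, and 1.33.5 looks at results overall and then by sex and BMI. All of these figures still pool over people. No section mentions a reference breath, a personal scale factor, within-person repeatability, or a split of error into between- and within-person parts.

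**The concern.** People may differ in how far the lower ribs move per litre inspired. Sensor placement may add to this, since 1.5 allows one or both sides at an approximate rib level. Such differences are stable within a sitting. Breath-to-breath variation is not.

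The two sources of error point to different next steps. If the first dominates, the sensor may be usable after a short calibration against a spirometer. If the second dominates, calibration will not help. Section 1.3 hopes that "a wearable motion sensor could serve as a substitute for incentive spirometry", and 1.8 makes a larger study depend on these results being successful, so the distinction matters for that decision. A single error figure pooled over people does not show it.

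The unstated split unit adds to the problem, because it decides whether the person-to-person part appears in the figure at all.

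**Working it through.** **Breath count.** Six volumes (1.2, 1.5, 1.26) × 3 repeats = 18, which reproduces the synopsis. Section 1.17.1 lists seven ("250mL, 500mL, 750mL, 1000mL, 1500mL, 2000mL, and 2500mL"), giving 7 × 3 = 21. The two lists must be reconciled; 1500 mL is in both. With about 30 participants, 30 × 18 = 540 breaths.

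**Model (assumed).** log(motion) = log(volume) + b + e, where b is a person effect with SD sb and e a breath effect with SD sw. The documents give neither SD. The error SD for a participant outside the training data is:
- uncalibrated: √(sb² + sw²)
- one reference breath: √2 · sw
- mean of three reference breaths: sw · √(4/3)
- one breath, shrunk toward the population scale: √(sw² + sb²sw²/(sb² + sw²))

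| sb | sw | Uncalibrated | One breath | Three breaths | One, shrunk |
|---|---|---|---|---|---|
| 0.30 | 0.10 | 0.316 | 0.141 | 0.115 | 0.138 |
| 0.20 | 0.10 | 0.224 | 0.141 | 0.115 | 0.134 |
| 0.20 | 0.20 | 0.283 | 0.283 | 0.231 | 0.245 |
| 0.10 | 0.20 | 0.224 | 0.283 | 0.231 | 0.219 |

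One unshrunk breath helps only if sb > sw, that is, if the between-person share of variance (ICC) exceeds 0.5. The mean of three helps if sb² > sw²/3, that is, ICC > 0.25. The shrunk version is never worse in this model when the variances are known.

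**In millilitres.** Simulation with multiplicative gain and noise, calibrated at 1500 mL and scored on the other five volumes, gives these mean absolute errors (approximate):

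| Gain CV | Noise CV | Uncalibrated | One breath | Three breaths |
|---|---|---|---|---|
| 30% | 10% | 305 | 142 | 115 |
| 20% | 10% | 220 | 142 | 115 |
| 20% | 20% | 278 | 286 | 230 |
| 10% | 20% | 220 | 286 | 229 |

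Hand check: the five scored volumes average (250 + 500 + 1000 + 2000 + 2500)/5 = 1250 mL, and for a normal error the mean absolute error is about 0.798 × SD. At these sizes a CV is close to a log SD. The first row gives 0.798 × 0.316 × 1250 = 315, then 141 and 115. The last row gives 223, 282 and 230.

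**Folds by breath.** Assume random 5-fold splitting of 540 breaths, 108 per fold. For a given test breath, the chance that both same-person, same-volume repeats are also in the test fold is (107/539) × (106/538) = 0.039. At least one is therefore in training with probability 0.96. If the model can recognise the wearer from about 18 × 0.8 = 14.4 training breaths, the error SD at sw = 0.10 falls to 0.10 × √(1 + 1/14.4) = 0.103. With sb = 0.30 the person-level figure is 0.316. The same data and sensor could thus report errors that differ threefold, depending on a choice the plan leaves open.

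**Can the study estimate the split?** With 30 × 18 breaths, the approximate 95% interval for the ICC is 0.38 to 0.65 at a true value of 0.5, and 0.71 to 0.88 at 0.8. That is precise enough to be informative.

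**The case against.** The strongest reply concerns scope. This is a proof-of-concept study in about 30 volunteers whose primary endpoint is a database. The waveforms are kept (1.37), so calibration could be studied later, and the protocol never claims a calibrated product. Person differences are already examined by sex and BMI. The repeats are not idle either: every retained waveform is used for fitting, validation or testing. All of this is fair, and it makes the point an inexpensive improvement rather than a fault that invalidates the study. It does not close the gap. Sex and BMI cannot capture differences among people alike in both, and a calibration scheme or split unit chosen after results are seen is open to selection.

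The rule against tuning on the test set is sound practice and is not criticised here. A scale factor fixed in advance, taken from reference breaths that are then left out of scoring, need not break it.

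A reader might infer that stable person differences will be counted as failure and a workable sensor rejected. The documents do not support that. Section 1.30 speaks only of accurate conversion, 1.33.2 ties primary success to data transmission, and no accuracy limit or rejection rule appears anywhere. The direction is also open: folds by breath, which the text permits, would make accuracy look better.

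**Conclusion.** The omission is real and its consequence is limited: the reported accuracy will be hard to interpret, by an amount and in a direction the plan does not fix. In the illustrations, one reference breath changes mean absolute error from about 305 to 142 mL in one case and from about 220 to 286 mL in another. It would be wrong to conclude that a single reference breath removes the person-to-person error. It replaces that error with the reference breath's own noise, which is a gain only when between-person variation is the larger.

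These sizes rest on assumed CVs, on motion proportional to volume with one scale per person, and, for the folds-by-breath result, on five folds and a model able to recognise the wearer. The absence of a stated split unit and of any calibration or repeatability analysis rests on the text alone.

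**What to change.** In 1.33.3:
1. State that all breaths of a participant stay in one fold.
2. Keep the uncalibrated error as the figure for a new wearer.
3. Add a separately labelled, pre-specified calibrated estimate. Use the held-out participant's 1500 mL breaths (one, then all available) to set a personal scale, with a version shrunk toward the population scale using variances from the training participants. Score only the other volumes, and report uncalibrated and calibrated error on the same scored breaths.
4. Among participants with repeats, report the within-person SD of predicted volume across repeats and the between/within-person variance split.

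The cost is analysis time and one extra result; no new data or participant burden is needed. Breaths used for calibration are not scored in that comparison. Participants with a single breath per volume, whom 1.7 allows, cannot contribute to the three-breath or repeatability figures, though a usable 1500 mL breath still lets them enter the one-breath estimate. The number contributing to each figure should be stated.

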1.33.4 Safety Analyses

N/A.

1.33.5 Sub-Group Analyses

Results will be analyzed as a whole and then based on sex and BMI to determine if these factors significantly impact chest wall motion corresponding to teach volume of inspiration.

1.33.6 Tabulation of individual Participant Data

De-identified participant data will be listed by measure and time point within our secure database; however, all data will be analyzed and presented as a group for further presentation or publication.

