1.5 OVERALL DESIGN

Healthy volunteers (n = 30) will be recruited for participation in this proof-of-concept study. Each participant will be consented and assigned a study number to ensure that all data is non-PII. Participants will be asked to fill out a de-identified form with their age, sex, height and weight prior to application of motion sensor (see section **1.6**).

Each participant will wear the devices for approximately 10-30 minutes while they perform a series of breathing exercises. The thoracic wearable will be adhered unilaterally or bilaterally at approximately the level of the 9th and 10th ribs at the mid-axillary line. Hypoallergenic double-sided tape will be used to adhere the motion sensor to the volunteers' torso in this position. The participant will ideally take three breaths through a traditional incentive spirometer while wearing the devices at each of the following volumes: 250mL, 500mL, 1000mL, 1500mL, 2000mL, and 2500mL. Each breath will be held for approximately 5 seconds before being released. Throughout this period, the thoracic wearable will be detecting chest wall expansion. All data will be transmitted to a secure server located within the NIH clinical center for analysis and model creation. Upon completion of the breathing exercises, the device will be removed from the participant, and the participant will be free to leave. There will be no further study visits or contact required.

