1.7 JUSTIFICATION FOR INTERVENTION

The entire duration of study participation is 10-30 minutes, making this an incredibly low-commitment study for healthy volunteers. Minimum acceptable study participation is completion of the demographic information at least one attempt of all measured lung volumes, as it is possible that some participants will not be capable of taking the maximal volume of inspiration.

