1.33 STATISTICAL ANALYSES

1.33.1 General Approach

Data will be transmitted from the motion sensors to a secure NIH server for storage. Motion data will be quality checked and corrupted waveforms will be removed. Waveforms corresponding to activity (motion artifacts) will also be removed, per standard signal processing techniques. The waveforms will then be parsed out by corresponding volume of inspiration. A customized model will be fine-tuned on these sequences, learning to recognize patterns in chest wall motion associated with each incentive lung volume. To ensure that the model is unbiased, class balancing will be performed for both demographic and clinical labels using majority undersampling techniques. The transformer model will be fine-tuned and validated on the subjects in the dataset. Once the model is fully developed from the data collected in this study, we will test it against the traditional incentive spirometry to calculate its accuracy.

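### Accuracy has no defined measure or unit, reporting is group-only, and no participant-level error or allowance for repeated breaths is planned

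*Combined protocol and SAP*

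**What the plan says.** All references are to the combined protocol and SAP.

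- **Level of reporting.** Section 1.33.6 has de-identified participant data listed in the database, but then states that "all data will be analyzed and presented as a group for further presentation or publication". The sentence covers analysis as well as presentation.
- **Accuracy.** Section 1.33.1 says that once the model is developed "we will test it against the traditional incentive spirometry to calculate its accuracy". No measure, unit, interval or threshold is given. Section 1.33.3 plans validation for each target volume with a cross-validation scheme such as stratified K-fold. It does not say whether folds are formed from people or from breaths.
- **Subgroups.** Section 1.33.5 asks whether sex and BMI significantly affect chest wall motion. It does not say how repeated breaths enter that comparison.
- **Number of people and breaths.** Section 1.5: "Healthy volunteers (n = 30) will be recruited for participation in this proof-of-concept study". Section 1.1: "healthy participants will complete a total of approximately 18 measured breaths through a traditional incentive spirometer".
- **Unequal contributions.** Three breaths per volume is only the ideal. Section 1.7 accepts "at least one attempt of all measured lung volumes". Section 1.33.1 adds: "Motion data will be quality checked and corrupted waveforms will be removed". Motion artefacts are removed as well. No removal rate is given.

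**The concern.** The secondary hypothesis (section 1.30) is that chest wall motion can be converted accurately to inspired volume. The background section imagines a sensor that might replace the incentive spirometer. Such a sensor is worn by one person at a time, so the spread of error between wearers is a main part of the feasibility answer. A group result can look acceptable while the algorithm fails badly in a minority.

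Two further questions are left open. The first is weighting. People will keep different numbers of breaths, and an average over breaths gives more weight to those who keep more. The second is dependence. Breaths from one person share body shape, sensor placement and breathing style, so 540 breaths do not carry the information of 540 independent observations. Sex and BMI are fixed within a person, so the comparisons in section 1.33.5 rest on about 30 independent units however many breaths are recorded.

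**Working it through.** **1. Breath counts.** The list in section 1.5 ("250mL, 500mL, 1000mL, 1500mL, 2000mL, and 2500mL") has six volumes, and 6 × 3 = 18. This reproduces the figure in the synopsis, and 30 × 18 = 540 breaths in all. The list in section 1.17.1 ("250mL, 500mL, 750mL, 1000mL, 1500mL, 2000mL, and 2500mL") has seven volumes, and 7 × 3 = 21, or 630 in all. That does not reproduce 18, and the two sections must be reconciled. The minimum is one attempt per volume: 6 breaths, or 7 on the longer list. The rest uses 18.

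The documents give no error size, ICC or breath-loss pattern. Everything below is an assumption chosen to show direction and order of size.

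**2. Hidden failures.** Assume 27 wearers with 95% accuracy and 3 with 40%, all keeping equal numbers of breaths. The group figure is (27 × 95 + 3 × 40)/30 = 89.5%. Nothing in that figure shows that one wearer in ten is badly served.

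**3. Weighting.** Assume 24 people with 150 mL error and 6 people with 450 mL error.

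- The average over people is (24 × 150 + 6 × 450)/30 = 210 mL, whatever breaths are kept.
- The average over breaths depends on who loses breaths:

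| Breaths kept | Calculation | Pooled error |
|---|---|---|
| All keep 18 | same as the person average | 210 mL |
| The 6 poor wearers keep 12, others 18 | (24×18×150 + 6×12×450)/504 | 193 mL |
| The 6 poor wearers keep 6, others 18 | (24×18×150 + 6×6×450)/468 | 173 mL |
| 6 of the good wearers keep 6, all others 18 | (18×18×150 + 6×6×150 + 6×18×450)/468 | 219 mL |

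The third row understates the person average by 1 − 173/210 = 18%. The first row shows no distortion, and the last goes the other way. The direction depends on whether breath loss is related to error.

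**4. Dependence and intervals.** Design effect = 1 + (18 − 1) × ICC. Effective number = 540/design effect. The 95% half-width is 1.96 × √(0.9 × 0.1/effective number) at an assumed accuracy of 90%. Treating 540 breaths as independent gives 2.5 points.

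| ICC | Design effect | Effective breaths | Half-width (points) |
|---|---|---|---|
| 0.05 | 1.85 | 292 | 3.4 |
| 0.1 | 2.7 | 200 | 4.2 |
| 0.3 | 6.1 | 89 | 6.2 |
| 0.5 | 9.5 | 57 | 7.8 |
| 0.8 | 14.6 | 37 | 9.7 |

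A beta-binomial simulation (20,000 runs, 30 people, 18 breaths each, true accuracy 90%) gave the coverage of nominal 95% intervals:

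| ICC | Breath-level interval | Person-level t interval |
|---|---|---|
| 0.1 | 77% | 93% |
| 0.3 | 57% | 91% |
| 0.5 | 47% | 90% |

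The person-level interval is also somewhat short of 95% with 30 people, but far closer. With 21 breaths the design effect runs from 2.0 to 17.0 over the same ICC range of 0.05 to 0.8, so the conclusion does not change.

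**5. Sex/BMI tests.** At one volume each person gives 3 breaths, so the design effect is 1 + 2 × ICC: 2.0 at ICC 0.5 and 2.6 at 0.8. A breath-level test at nominal 5% then has a false-positive rate of 2 × [1 − Φ(1.96/√2.0)] = 17%, or 22% with 2.6.

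**The case against.** The strongest reply is that much of this is silence, not a stated plan. A reader might infer that the plan fixes on one accuracy figure over all breaths. The documents do not say so: section 1.33.3 plans validation per volume, and section 1.33.5 looks at sex and BMI. Nor does any section specify breath weighting or a breath-level interval. This stands, and the criticism is of what is left undefined. Even so, a breakdown by volume, sex or BMI does not show how error varies from wearer to wearer.

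A reader might also infer that pooling is biased towards people whose signal is easy to record. That needs retained breath count to be related to error, which the documents do not show. Section 1.7 explains the one-attempt minimum by inability to reach the largest volume, not by poor signal. The bias is possible, not established.

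Section 1.33.6 can also be read as a privacy statement, and most of the remedy (medians, quartiles, intervals) is itself group reporting. One might be tempted to say that the restriction protects nobody. The documents do not support that: there are about 30 people at one site, recruited by word of mouth, and staff and study-team relatives may enrol. Section 1.36.1 promises that shared data cannot be traced to a person. Individual plots therefore need the safeguards of that section. If privacy was the only intent, though, the rule need not extend to analysis.

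Finally, accuracy belongs to the secondary endpoint of a small proof-of-concept study, and larger evaluation is left to a new protocol. That limits the weight of the point. But section 1.8 makes the new protocol depend on success here, so the accuracy result should be interpretable.

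**Conclusion.** The point holds as a gap in the plan. The accuracy measure and its unit are undefined, section 1.33.6 sets a group-only rule, and nothing provides for error per participant, participant weighting or repeated breaths. Following the plan as written would leave the secondary hypothesis poorly answered, because the variation between wearers need never appear.

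The size cannot be determined from the documents. Under the assumed inputs, pooling could understate error by about 18%, leave it unchanged or slightly overstate it, depending on who loses breaths. The loss of precision is less dependent on particular choices: even an ICC of 0.1 brings the coverage of a breath-level 95% interval down to about 77%. This applies only if such an interval or test is computed, which the plan neither states nor rules out. It is a worthwhile, inexpensive correction and does not affect the primary endpoint, which is the database.

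**What to change.** Amend section 1.33.6, with a cross-reference in sections 1.33.1 and 1.33.3, to read:

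> Held-out error is calculated within each participant and averaged over participants with equal weight. Its distribution over participants (median, quartiles, range) is reported, with de-identified per-participant error shown where the data-sharing safeguards in 1.36.1 allow. Confidence intervals and the sex/BMI comparisons treat the participant as the independent unit (participant-level resampling or a participant random effect).

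Section 1.33.1 should also name the error measure, and the breath lists in sections 1.5 and 1.17.1 must be reconciled so that the intended number of breaths per person is clear. For the held-out error to describe a new wearer, the folds in section 1.33.3 must keep all of a person's breaths together, and this should be stated.

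The cost is SAP wording and a few lines of code, settled before results are seen. No new data, visits or participants are needed. The drawback is that the headline error will probably be larger and its interval wider.
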